3.2 Study Procedures

A schedule of study activities is presented in [Table 2](#). Following randomization, subjects will receive diet and exercise counseling on maintaining an appropriate healthy diet with a recommended initial caloric deficit of approximately 500 kcal per day and at least 30 minutes of regular physical activity on most days of the week. The total duration of study treatment will be 8 weeks (4 weeks of dose titration and 4 weeks of treatment at the assigned dose) with 24-hr ABPM recordings performed at Baseline/Randomization and again at Week 8/End of Study or Early Termination. Clinic visits will occur at Screening, Baseline/Randomization (2-day outpatient visit), Week 4, and Week 8/End of Study or Early Termination (2-day outpatient visit). The 24-hr ABPM data will be collected and transferred to the data management/biostatistics vendor for analysis in a blinded manner prior to study unblinding, using validated software.

In order to minimize the potential confounding of study results by changes in other medications, all concomitant medications, particularly those for management of blood pressure or other weight-related comorbidities, will be fixed in number, dose, and frequency for the duration of the study unless specific “rescue” criteria are met for blood pressure ($\geq 160/100$ mmHg, or $\leq 100/60$ mmHg and symptoms of hypotension). Any changes in concomitant medication will be fully documented.

Table 2 Schedule of Events

	Screening	Baseline/ Randomization ¹		End of Titration	End of Study or Early Termination	
Study Week	Week -4	Week 0		Week 4	Week 8	
Visit # (window in days)	1	2A ² (+3)	2B ²	3(± 3)	4A ² (± 3)	4B ²
Informed Consent	X					
Demographics	X					
Medical History	X					
Inclusion/Exclusion	X	X				
Weight	X	X		X	X	
Height, BMI	X					
Physical Exam	X					X
Vital Signs	X	X ³		X	X ³	X
Prior/Concomitant Medications ⁴	X	X	X	X	X	X
Adverse Events ⁵		X	X	X	X	X
Chemistry (Full Panel)	X					X
Chemistry (Limited Panel)				X		
Hematology/Lipids/HbA1c	X					X
TSH	X					
HIV, HCV, HBsAg	X					
Urinalysis	X					X
Urine Cotinine and Urine Drug Screen	X					
PK trough sample (prior to dosing)					X	
Urine pregnancy (WOCBP) / Contraception Reminder	X	X		X	X	

VIVUS LLC
 OB-409 Statistical Analysis Plan (Final, 27 April 2023)

24-hr ABPM Recording - Begin		X			X	
24-hr ABPM Recording – End & Removal			X			X
ABPM Device Instruction		X			X	
12-Lead ECG	X					X
Lifestyle counseling			X	X		
Contact RTSM	X		X	X		
Randomization			X			

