4.3 Exploratory Endpoints

The exploratory endpoints of the study are:

- Mean hourly changes in SBP and DBP from baseline to Week 8, defined as the mean change from baseline at each hour;
- Change in mean daytime and nighttime SBP as measured by 24-hr ABPM from baseline to Week 8;

- Change from baseline to Week 8 in nighttime “dipping” of SBP, and the percentage of subjects with a normal SBP “dipping” pattern at Week 8. A normal “dipping” pattern of SBP will be defined as a reduction of mean nighttime SBP of $\geq 10\%$ relative to mean daytime SBP during the same 24-hr recording;
 - SBP dipping is calculated as: $100 \times [(\text{mean daytime SBP} - \text{mean nighttime SBP}) / \text{mean daytime SBP}]$
- Change from baseline to Week 8 in nighttime “dipping” of DBP, and the percentage of subjects with a normal DBP “dipping” pattern at Week 8. A normal “dipping” pattern of DBP will be defined as a reduction of mean nighttime DBP of $\geq 10\%$ relative to mean daytime SBP during the same 24-hr recording;
 - DBP dipping is calculated as: $100 \times [(\text{mean daytime DBP} - \text{mean nighttime DBP}) / \text{mean daytime DBP}]$
- Percentage of subjects meeting the following BP thresholds at baseline and Week 8 as measured by 24-hr ABPM;
 - SBP: ≥ 160 mmHg for 2 consecutive readings; ≥ 180 mmHg for 2 consecutive readings;
 - DBP: ≥ 100 mmHg for 2 consecutive readings; ≥ 110 mmHg for 2 consecutive readings;
- Percentage of subjects with the average of three successive BP meeting the following thresholds at baseline and each post-baseline visit as measured in clinic;
 - SBP: ≥ 160 mmHg; ≥ 180 mmHg; ≥ 20 mmHg increase from baseline;
 - DBP: ≥ 100 mmHg; ≥ 110 mmHg; ≥ 15 mmHg increase from baseline;
- Change from baseline to Week 8 in mean 24-hr heart rate, mean daytime heart rate, mean nighttime heart rate, and mean hourly heart rate;
- Percentage of subjects meeting the following heart rate thresholds at baseline and Week 8 as measured by 24-hr ABPM;
 - > 100 bpm for 2 consecutive readings; > 100 bpm for at least 1 hour; > 100 bpm for at least 2 hours; > 100 bpm for at least 3 hours; > 100 bpm for at least 4 hours; mean daytime heart rate > 100 bpm;
- Percentage of subjects meeting the following heart rate thresholds at baseline and each post-baseline visit as measured in clinic;
 - > 100 bpm;
 - ≥ 10 bpm increase from baseline; ≥ 20 bpm increase from baseline

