5.4 Per Protocol (PP) Population

PP Population will be comprised of ITT subjects who met all of the following criteria:

- Compliant to study treatment (defined as $\geq 80\%$ treatment compliance as specified in [Section 6.5](#));
- Last daily dose of study drug administered on the same date that ABPM was initiated at Visit 4A (first day of Week 8/End of Study or Early Termination);
- Had at least 23.5 hours of ABPM data (i.e. blood pressure and heart rate data) at baseline and at Week 8/End of Study or Early Termination, and at least 75% of 24-hr ABPM readings (or equivalently 48 readings during the 24-hr period) are not missing;
- Subjects with any major protocol deviation that had impact on ABPM readings will be excluded from the PP Population.

The PP population will be used to assess the primary and secondary endpoints as primary analyses. Subject inclusion in the PP population will be determined and documented prior to database lock and treatment unblinding.

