7.2.2 Analyses of Secondary Endpoints

Secondary endpoints including change from baseline to Week 8 in mean DBP as measured by 24-hr ABPM, mean change in SBP and DBP from baseline to Week 8 as measured in clinic will be analyzed for the PP population using a similar ANCOVA model structure as that of the primary analysis. The model will comprise of treatment, stratification factors (sex, age and hypertensive status) and baseline value of the dependent variable as a covariate. Adjusted means (LS Mean \pm standard error) with associated two-sided 95% confidence intervals for the between-treatment comparisons and for the changes from baseline will be reported.

The estimand, estimator, and estimate of these secondary endpoints are defined as follows:

Estimand	Population	Per Protocol
Endpoint		Changes from Baseline in Variable X at Week 8

	How to account for intercurrent events	The treatment policy strategy will be followed, whereby the observed value (if not missing) for the endpoint of interest will be used for analysis.
	Population-level summary	The between-treatment difference in changes from baseline to Week 8 in Variable X.
Estimator	Analysis	ANCOVA with treatment, stratification factors (sex, age and hypertensive status) and baseline value of variable X as a covariate.
Estimates	Primary to support the estimand	Between-group comparison (effect in VI-0521 minus effect in placebo [or phentermine]): 
 ✓ LSM for the between-group difference ✓ 95% CI of the LSM ✓ p-value
Estimates	Tributary	Within-treatment group comparison (effect at Week 8 minus the value at baseline): 
 ✓ LSM for the within-group difference ✓ 95% CI of the LSM ✓ p-value

Similar imputation method as described in [Section 7.2.1](#) will be carried out for missing DBP values from the 24-hr ABPM. For missing clinic SBP and DBP, data will not be imputed after mapping unscheduled visits.

Additionally, supportive analysis of the 24-hr mean DBP endpoint will be carried out similarly as described in [Section 7.2.1.2](#). Supportive analysis of the clinical SBP and DBP endpoint will be performed using the observed case data for the ITT population. Extra sensitivity analyses similar to the primary endpoint may be conducted on the secondary endpoints if applicable.

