7.2.3 Analysis of Exploratory Endpoints

Analysis of exploratory endpoints will be performed on the PP population using the observed case data.

All change from baseline exploratory endpoints will be analyzed using ANCOVA models in a similar manner to the primary and secondary endpoints. For the endpoints on percentage of subjects with a normal SBP and DBP ‘dipping pattern’ at Week 8, a Cochran-Mantel-Haenszel (CMH) χ^2 test that is stratified by sex, age and hypertensive status will be used for analysis. Corresponding estimates of the common Mantel-Haenszel relative risk will be provided along with 95% confidence intervals (CIs). For the endpoints on percentage of subjects meeting the BP or heart rate thresholds, descriptive summary will be provided.

Example SAS codes for CMH test are:

No sensitivity analysis is planned for the exploratory endpoints.

In addition, all 24-hr ABPM measurements including blood pressure and heart rate that are summarized in the endpoints will be presented in a listing.

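### SAP 7.2.3 tests normal dipping at Week 8 without using baseline dip, which costs some precision on an exploratory endpoint but does not bias it

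*SAP*

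**What the plan says.** SAP 4.3 lists two quantities for each pressure: the change in dip from baseline to Week 8, "and the percentage of subjects with a normal SBP" dipping pattern at Week 8 (and the same for DBP). A dip is normal if it reaches 10%.

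SAP 7.2.3 handles the two differently.

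- **Change in dip.** "All change from baseline exploratory endpoints will be analyzed using ANCOVA models in a similar manner to the primary and secondary endpoints". In SAP 7.2.2 that model carries the "baseline value of the dependent variable as a covariate".
- **Normal pattern at Week 8.** A CMH "test that is stratified by sex, age and hypertensive status will be used for analysis", with a common Mantel-Haenszel relative risk and 95% CI. Baseline dip is not a stratum. The example code is blacked out, so only the text could be checked.

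The baseline information is collected: SAP 3.2 has "24-hr ABPM recordings performed at Baseline/Randomization and again at Week 8/End of Study or Early Termination". On the analysis set, SAP 7.2.3 states: "Analysis of exploratory endpoints will be performed on the PP population using the observed case data". One entry criterion for that set, in SAP 5.4, is: "Had at least 23.5 hours of ABPM data (i.e. blood pressure and heart rate data) at baseline and at Week 8/End of Study". The criterion also covers an early-termination visit and requires 75% or more of the readings to be present. SAP 7.2.3 plans no sensitivity analysis for exploratory endpoints.

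**The concern.** A subject's dip at baseline is likely to predict whether the dip is normal at Week 8. The planned test leaves that information out, although it costs nothing more to collect and the same section uses it for the continuous version of the endpoint. The SAP gives no reason for the difference.

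What is at stake is the width of the confidence interval for the relative risk and the power of one exploratory comparison. Adjustment would also take account of any chance difference between arms in baseline dippers.

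**Working it through.** **Inputs from the documents.** There are 185 subjects per group with 5% drop-out (SAP 8), and 2 × 2 × 3 = 12 strata (SAP 3.3). The SAP's sample size is for the primary endpoint and reproduces: n = 2 × (1.960 + 0.842)² × 10² / 3² = 174.4, so 175, and 175 / 0.95 = 184.2, so 185. After drop-out, 185 × 0.95 = 175.75, taken as 176 per arm. The per-protocol set may be smaller. That would lower the power figures below but hardly change the variance ratios.

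**Is baseline dip available?** The schedule gives 16 h × 3 + 8 h × 2 = 64 readings, and 75% of 64 is the SAP's 48. Up to 16 readings may be missing, so a subject could in principle lack the night readings. Baseline dip should therefore be computable for essentially all per-protocol subjects, though this is not guaranteed for each one.

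**Assumptions.** The documents give no dipping rate, no SD of dip and no correlation between baseline and Week 8 dip. Two assumed scenarios were simulated with jointly normal dips and 176 per arm:

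- A: mean dip 10, SD 7, a shift of 2 points. The share with a normal dip is 50% against Φ(2/7) = 61%, a difference of about 11 points.
- B: control rate 50% or 30%, plus 15 points on treatment, with the strata explaining 5% of the variance.

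**Like-for-like comparison.** Logistic regression with the stratification factors was fitted with and without continuous baseline dip, and the estimates were standardised. Reduction in variance:

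| Correlation | A: risk difference | B: log risk ratio, 50% v 65% | B: log risk ratio, 30% v 45% |
|---|---|---|---|
| 0.3 | 6% | 5% | 4% |
| 0.4 | 12% | 7% | 7% |
| 0.5 | 15% | 11% | 13% |
| 0.6 | 23% | 21% | 19% |

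Repeat runs of A span about 5% to 25%, with 2 to 12 points more power. In B (50% v 65%), power goes from 82% to 84% at 0.3, 84% to 87% at 0.4, 82% to 87% at 0.5 and 83% to 91% at 0.6. At a correlation of 0.2 the variance reduction in B is only 1% to 2%.

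**Separating covariate from method.** In one run of A at correlation 0.3, power was 54.7% for CMH, 55.9% for logistic regression without baseline dip and 58.5% with it. Of the 3.8-point gain, 1.2 points (about a third) come from leaving CMH and 2.6 from the covariate. A direct comparison of CMH with the adjusted model therefore overstates what baseline contributes.

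**Can the gain be had inside CMH?** Adding baseline dipper status (yes/no) makes 24 strata. In B (50% v 65%), the variance of the log relative risk relative to the planned 12 strata is 1.02 at correlation 0.2, 1.00 at 0.3, 0.98 at 0.4, 0.93 at 0.5 and 0.85 at 0.6. Subjects in strata that contain only one arm rise from about 1 to about 5 of 352. At low correlation there is no gain.

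**Validity.** Type I error stayed near 5% for the planned CMH test and for the adjusted model.

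**The case against.** The case for leaving the plan alone is strong in three respects.

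1. **CMH has a basis.** Protocol 13.1.5 asks for a non-parametric method for categorical outcomes, and the strata are the randomisation factors. A reader might infer that baseline was left out for no reason. The documents support only that no reason is stated. Protocol 13.1 lets the SAP modify methods, so adding a model is open to the sponsor, but this is an argument for keeping CMH and not replacing it.
2. **Baseline dip is already used where it helps most.** For change in dip, the ANCOVA standard error under scenario A is 7 × √(2(1 − r²)/176). At r = 0.3 this is 0.712, and 2/0.712 = 2.81 gives 80% power. At 0.4, 0.5 and 0.6 power is 83%, 87% and 92%. That exceeds what adjusted logistic regression reaches on the dichotomised endpoint (about 58% to 68% across runs). This stands, but it does nothing for the reported relative risk and its interval.
3. **The stakes are low.** The endpoint is exploratory, outside the hierarchy in SAP 7.1.2.1, and has no power target.

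A reader might also infer that chance imbalance in baseline dippers biases the relative risk. It does not: under randomisation the test and interval already allow for it. Nor would a disagreement between the two dipping analyses have to come from adjustment, since one concerns a mean change and the other a threshold. And the test does not rest on Week 8 status with no adjustment at all, because sex, age and hypertensive status are in it.

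**Conclusion.** The point holds as a modest matter of efficiency. The planned CMH analysis is valid but leaves out a baseline value that is collected for essentially all analysed subjects. Adjusting for continuous baseline dip would lower the variance of the risk difference by about 5% to 25% if the correlation between baseline and Week 8 dip is 0.3 to 0.6. The gain is small below about 0.5. The correlation, the SD and the dipping rates are all assumptions, so the direction is more certain than the size. No primary or secondary conclusion is affected.

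A related point must be settled first for DBP. SAP 4.3 defines a normal DBP dip relative to mean daytime SBP, while its formula divides by mean daytime DBP. Protocol 7.3 and 13.1.5 match SAP 4.3, but the protocol synopsis refers to daytime DBP. As SAP 4.3 stands, Week 8 DBP status and a baseline DBP dip taken from the formula would rest on different denominators.

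**What to change.** In SAP 7.2.3:

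- Keep the CMH test and the Mantel-Haenszel relative risk as planned.
- Add a prespecified supportive logistic regression for normal dipping at Week 8, separately for SBP and DBP, with treatment, sex, age group, hypertensive status and baseline dip as a continuous percentage. Report the standardised (marginal) risk ratio and risk difference with 95% CI, and state how the interval is obtained (delta method or bootstrap).
- Use continuous baseline dip. Do not add dipper status as a further CMH stratum, which gains nothing at low correlation.
- Reword the statement that no sensitivity analysis is planned for exploratory endpoints, so that it allows for this model.

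In SAP 4.3, and in the matching protocol sections, reconcile the DBP normal-dip definition with the DBP dip formula before the model is specified.

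The cost is a sentence or two in the SAP and a few lines of code. The downside is small: a standardisation step and one more reported estimate beside the Mantel-Haenszel relative risk.

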7.2.4 Pharmacokinetic Analyses

PK blood samples will be collected at the end of the study and will be used to obtain the PK profile of phentermine and topiramate levels. The concentration data will be summarized descriptively by treatment group.

7.3 Safety Analyses

All safety analyses will be performed on the Safety population.

7.3.1 Adverse Events

Adverse events (AEs) are defined as any untoward medical occurrences in subjects administered the study treatment, whether or not they have a causal relationship to the treatment. All reported terms (investigator descriptions) for AEs will be coded using the most recent version of the MedDRA. TEAEs are defined as any AEs that occurred or worsened after the first randomized study medication; regardless of on-treatment or off-treatment periods. All TEAEs will be summarized with frequencies and percentages of subjects by treatment group, system organ class (SOC), and preferred term (PT). The frequencies and percentage of subjects with any AE across all SOCs will be summarized by treatment group. The AEs occurring prior to receiving the first randomized dose are defined as pre-treatment AEs and will be listed only.

TEAEs leading to discontinuation of study drug, TEAEs related to study drug, serious TEAEs, and TEAEs by maximum severity will be summarized and listed. Deaths will be listed if any. An overall summary of the above categories by treatment group will also be provided. All AEs leading to discontinuation from study, serious AEs, and death will be provided in listings.

TEAEs of special interest including AEs that require initiation or modification of antihypertensive therapy will be summarized separately, if applicable.

7.3.2 Clinical Laboratory Evaluations

All hematology, fasting blood chemistry, lipid panel, urinalysis and other lab results will be listed, including scheduled and unscheduled/repeat measurements (if any). Laboratory

assessments that are outside of normal ranges and/or with potential clinical significance will be considered an abnormal value and flagged in the listings.

Baseline values, values at post-baseline visits, and change from baseline values will be summarized descriptively for all laboratory parameters with numerical measures by treatment. Additionally, shift tables will be generated to summarize the normal and abnormal (abnormal high and abnormal low) status change from baseline to post-baseline visits. The frequency and percentage of subjects with laboratory results above or below the normal range and threshold limits at each scheduled assessment or any time during the treatment will be summarized by treatment group. All laboratory measurements that are collected from unscheduled visits will be mapped according to the visit window defined in [Section 7.1.5](#). Data from any unscheduled visits that are not be able to mapped to a scheduled visit will not be summarized in the by-visit descriptive tables, but will be included in the assessment when summarizing the worst case scenario, e.g., abnormality status.

Laboratory tests are shown in the table below.

Hematology	Fasting blood full chemistry	Pregnancy Testing

• hemoglobin• hematocrit• red blood cell count• total white blood cell count• white blood cell differential (neutrophils, lymphocytes, monocytes, eosinophils, and basophils)• platelet count	
• albumin• alkaline phosphatase• ALT• AST• blood urea nitrogen• serum calcium• serum chloride• serum sodium• bicarbonate• creatinine (and estimated creatinine clearance)• gamma-glutamyl transpeptidase (GGT)• glucose• lactate dehydrogenase• serum phosphorus• serum potassium• total and direct bilirubin• total protein• uric acid• total cholesterol• triglycerides• LDL-C• HDL-C• TSH (at screening only)• HbA1c	
• Urine pregnancy test (WOCBP)
		Urinalysis
		
• midstream urinalysis with reflex microscopic evaluation
		Urine Drug Screen (Screening Only)
		
• cannabinoids• amphetamines• cocaine• barbiturates• benzodiazepine• opiates
		Serology (Screening only)
		
• HBsAg• HCV• HIV
		Urine Cotinine (Screening Only)
		PK sample (End of Study Only)
		
• Phentermine• Topiramate
Limited chemistry panel: sodium, potassium, chloride, bicarbonate, BUN, creatinine, glucose.		

7.3.3 Vital Signs

Baseline values, values at post-baseline visits, and change from baseline values will be summarized descriptively by treatment group and visit for the Safety Population. Vital signs parameters include systolic blood pressure, diastolic blood pressure, heart rate, respiration rate, temperature. For blood pressure, the average of three successive readings will be used for summary. All vital signs data will be presented in a listing.

7.3.4 Physical Examination

Physical examination will be done at Screening and Week 8/End of Study or Early Termination visits. The results will be provided in a listing. Abnormal physical exam findings will be summarized descriptively by treatment group, if applicable.

7.3.5 Electrocardiogram Findings

ECG will be performed at Screening and Week 8 or early termination visits. ECGs will be evaluated for arrhythmias, conduction disturbances, or other clinically relevant changes during the study period. Changes from baseline of the ECG will be summarized descriptively by treatment group at each visit for heart rate, RR interval, PR interval, QRS interval and QT interval. The number of subjects with clinically significant ECG abnormalities will also be summarized by treatment group and visit. All ECG data will be included in the listing.

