Phentermine, as a sympathomimetic agent, has been a subject of concern for possible cardiovascular adverse reactions such as tachycardia or elevation of blood pressure. Although mechanistically, these effects could be caused by an imbalance of cardiovascular autonomic function due to increased sympathetic nerve tone, it is likely that the selective release of norepinephrine within the hypothalamus with little or no dopamine or 5-hydroxytryptamine activity provides a rational basis for it having minimal cardiovascular effects at therapeutic doses.⁴ In a clinical trial evaluating multiple dose levels of phentermine, topiramate, and combinations of these agents, phentermine given at daily doses of 7.5 mg and 15 mg for 6 months produced modest increases in heart rate compared to placebo, but no increases in systolic or diastolic blood pressure.⁵ When phentermine was given in combination with topiramate, increases in heart rate were still observed at the top dose level, but clinically meaningful decreases in both systolic and diastolic blood pressure (BP) compared to placebo were achieved.^{2,3,5,6}

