6.0 TRIAL DESIGN

This randomized, double-blind, placebo and active comparator-controlled study will be conducted at about 35 sites in the US. Approximately 555 eligible subjects will be randomly assigned with equal probability, to daily treatment with top-dose VI-0521 (phentermine and topiramate extended-release capsules 15 mg/92 mg), phentermine 30 mg, or placebo (1:1:1 ratio; 185 subjects per group). Stratification factors include gender (male; female), age (< 50; ≥ 50 years), and hypertensive status (no medical diagnosis of or treatment for hypertension; medical diagnosis of hypertension treated with 0-2 antihypertensive agents; or medical diagnosis of hypertension treated with 3 or more antihypertensive agents).

Subjects will undergo a four-week titration period with weekly dose increases until the randomized dose is reached ([Section 9.4.1](#)).

Following randomization, subjects will receive diet and exercise counseling on maintaining an appropriate healthy diet with a recommended initial caloric deficit of approximately 500 kcal per day and at least 30 minutes of regular physical activity on most days of the week. The total duration of study treatment will be 8 weeks (4 weeks of dose titration and 4 weeks of treatment at the assigned dose) with 24-hr ABPM recordings performed at baseline/randomization and again at Week 8/end of study or early termination. Clinic visits will occur at Screening, Baseline (2-day outpatient visit), Week 4, and Week 8/end of study (2-day outpatient visit). The 24-hr ABPM data will be read and analyzed in a blinded manner by a central reader, using validated software.

In order to minimize the potential confounding of study results by changes in other medications, all concomitant medications, particularly those for management of blood pressure or other weight-related comorbidities, will be fixed in number, dose, and frequency for the duration of the study unless specific “rescue” criteria are met for blood pressure ($\geq 160/100$ mmHg, or $\leq 100/60$ mmHg and symptoms of hypotension). Any changes in concomitant medication will be fully documented.

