11.7 Electrocardiograms

Twelve-lead ECG assessments will be performed at screening, and end of study or early termination visits. ECGs will be evaluated for clinically significant abnormalities that would prevent entry into the study, and for arrhythmias, conduction disturbances, or other clinically relevant changes between randomization and each of the subsequent evaluations. Parameters including heart rate, R-R, P-R, QT intervals, and QRS duration will be recorded.

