4.4 Safety Endpoints

The safety endpoints include evaluation of the following:

- Adverse events (AEs)
- Changes in laboratory parameters
- Changes in Electrocardiograms (ECG)
- Physical exam findings
- Vital signs
- Requirement for rescue therapy for blood pressure and type 2 diabetes mellitus (T2DM)

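### The ECG safety summary uses QT without rate correction, although the protocol reports heart-rate rises with phentermine and with the top-dose combination, so a QT prolongation against placebo could be partly or fully masked

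*SAP*

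**What the plan says.** SAP 4.4 and Protocol 7.4 list ECG changes among the safety evaluations. SAP 7.3.5 specifies descriptive summaries of change from baseline "by treatment group at each visit for heart rate, RR interval, PR interval, QRS interval and QT interval". It adds: "The number of subjects with clinically significant ECG abnormalities will also be summarized by treatment group and visit". All ECG data go into a listing. No numeric QT criterion is attached to the count of abnormalities.

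Protocol 11.7 deals with what is collected: "Parameters including heart rate, R-R, P-R, QT intervals, and QRS duration will be recorded". Both ingredients of a rate correction are therefore on hand. No corrected QT, correction formula or QT threshold appears in either document.

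On heart rate, Protocol 4.1 describes an earlier trial in which phentermine at 7.5 and 15 mg daily "for 6 months produced modest increases in heart rate compared to placebo, but no increases in systolic or diastolic blood pressure". For the combination with topiramate, it says that "increases in heart rate were still observed at the top dose level". In this trial one arm receives phentermine 30 mg, one receives VI-0521 15/92 mg (15 mg of phentermine), and one receives placebo.

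ECGs are taken at Screening and at the end of study or early termination (Protocol Appendix 1). The last dose is given at Visit 4A and the ECG is done at Visit 4B, about a day later (Protocol 10.4).

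**The concern.** The QT interval shortens as the heart beats faster, whatever happens to repolarisation. That matters little if heart rate is balanced between arms. Here the sponsor's own background section gives reason to expect imbalance, and the imbalance would be caused by treatment. Randomisation balances baseline heart rate; it does not remove a rate difference that the drug produces.

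If heart rate is higher in an active arm at the end-of-study ECG, the difference from placebo in change in raw QT combines two things: shortening due to rate, and any drug effect on repolarisation. The first pulls the estimate downwards, which is the direction that looks safe. A table of raw QT could then understate a prolongation or fail to show it.

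At stake is how the QT row of a descriptive safety table can be read. No hypothesis test is attached to it.

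**Working it through.** **Inputs from the documents.** QT and R-R are both recorded (Protocol 11.7). Change in raw QT is summarised (SAP 7.3.5). The direction of the heart-rate effect is upward with phentermine and with the top-dose combination, with no bpm figure and nothing specific to 30 mg (Protocol 4.1). The plan states no QT or QTc figure, so there is none to reproduce.

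**Assumptions, not in the documents.** Resting rate 70 bpm, a baseline QT or QTcF of 400 ms as stated in each step, and the Fridericia relation QT = QTcF × RR^(1/3), with RR = 60/HR in seconds.

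**Step 1: shift in raw QT from rate alone.** Hold QTcF constant, start from raw QT = 400 ms, and let the rate rise by d bpm:

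shift = 400 × (70/(70 + d))^(1/3) − 400

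| Rise d (bpm) | Shift in raw QT (ms) |
|---|---|
| 1 | −1.9 |
| 2 | −3.7 |
| 3 | −5.6 |
| 5 | −9.1 |

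**Step 2: how much of a true prolongation remains visible.** Take baseline QTcF = 400 ms at 70 bpm, so raw QT = 400 × (60/70)^(1/3) = 380.0 ms. Add a true QTcF prolongation of 10 ms:

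change in raw QT = 410 × (60/(70 + d))^(1/3) − 380.0

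| Rise d (bpm) | Change in raw QT (ms) | Change in QTcF (ms) |
|---|---|---|
| 2 | +5.9 | +10 |
| 5 | +0.6 | +10 |
| 10 | −7.5 | +10 |

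A small rise hides part of the prolongation, a rise of about 5 bpm hides nearly all of it, and a larger rise reverses its sign.

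**Step 3: sensitivity to the assumptions.** With QTc 400 ms and baseline rates from 65 to 80 bpm, a rise of 1 to 10 bpm alone lowers raw QT by about 1.5 to 18 ms under Fridericia. Under a square-root (Bazett) relation the range is about 2 to 27 ms. With a true 10 ms QTcF prolongation and a 5 bpm rise, the change in raw QT lies between about 0 and +1.6 ms across those baseline rates (Fridericia). The direction is the same throughout; the size depends on a rate rise that the documents do not quantify.

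**The case against.** The strongest reply is that the rate shift is not hidden. SAP 7.3.5 tabulates heart rate and RR by arm next to QT, counts clinically significant abnormalities, and lists every ECG, so anyone could compute a corrected QT later. This is fair, and it limits the consequence. Two things remain. Group means of QT and RR do not give each subject's corrected value, so the planned tables show no individual outliers; the abnormality count has no QT criterion and relies on the reader's judgement. And a formula and cut-offs chosen after unblinding are post hoc.

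Second, the size is unknown. Protocol 4.1 calls the monotherapy increases modest, and the ECG about a day after the last dose may catch less of the rate effect than one nearer peak. That stands: the millisecond figures are illustrations, not predictions.

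Third, this is a blood-pressure trial and the ECG analysis is descriptive. That also stands.

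Three stronger readings are tempting and not supported:
- A reader might infer that the raw QT table is bound to show shortening or no change even if corrected QT lengthens. It does so only if the rate effect is at least as large as the prolongation; in Step 2, +10 ms with a 2 bpm rise still reads +5.9 ms.
- A reader might infer that the distortion always favours both active arms. It applies to comparisons with placebo, and only if the rate is raised at that ECG. For VI-0521 against phentermine 30 mg, the documents do not give the relative rate effects, so the direction is unknown.
- A reader might infer that the protocol itself prescribes an analysis of raw QT. Protocol 11.7 only says what is recorded, in a list that is not exhaustive, so a machine-derived QTc may be captured. The QT summary comes from SAP 7.3.5, which plans no corrected value.

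**Conclusion.** The point holds as a conditional one. The only QT measure in the planned summaries is uncorrected, and the protocol gives its own reason to expect a higher heart rate on phentermine and on the top-dose combination. If that rise is present at the end-of-study ECG, the comparison of raw QT with placebo is biased towards reassurance and could mask a prolongation in part or in full. On the assumed values (70 bpm, QT 400 ms, Fridericia), 1 to 5 bpm corresponds to about −1.9 to −9.1 ms; the timing of the ECG may make the actual shift smaller.

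The absence of a corrected QT is certain; the amount of masking is not. A reader might also infer that adding QTcF would let the trial declare repolarisation unaffected. It would not by itself: there is one scheduled post-baseline ECG, about 24 hours after dosing, compared with a screening ECG taken up to four weeks before baseline. The correction removes an avoidable confounder from a descriptive safety table and does no more than that. The primary endpoint, type I error and power are not affected.

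**What to change.** In SAP 7.3.5:

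- Derive QTcF = QT / (RR in seconds)^(1/3) for each ECG from that ECG's own QT and R-R, not from group means.
- Summarise QTcF and its change from baseline by arm in the same table as raw QT, heart rate and RR. Raw QT can stay.
- Add categorical counts by arm for absolute QTcF and for increase from baseline. Write the cut-offs into the SAP before unblinding. If unblinding has already taken place, label the counts as post hoc and document the addition in the study report, as SAP section 1 requires for deviations.
- State in the table notes that the ECG was taken about 24 hours after the last dose and that baseline is the screening ECG.

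The cost is one derived variable and a few table rows. No visit, procedure or data field is added, and no other analysis changes.
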